5.3. Secondary Objectives - Immunogenicity

To evaluate the immunogenicity of three different doses of the full length single chain (FLSC) gp120-CD4 complex vaccine assessed by the following parameters: 1) anti-FLSC antibodies, and 2) anti gp-120 (BaL), and 3) competitive antibodies titers to CD4i epitopes.

6. INVESTIGATIONAL PLAN

6.1. Overall Study Design

This will be a randomized, placebo-controlled, modified double-blinded study in 60 healthy adult volunteers. The study will evaluate the safety and immunogenicity of the full length single chain (FLSC) gp120-CD4 complex vaccine formulated with alum at three different doses. The study will have 3 arms as outlined below in Figure 1 and will last for 336 days (48 weeks). Volunteers will be immunized on Day 0, Day 28(4 weeks), Day 56(8 weeks), and Day 168(24 weeks).

6.1.1. Study Procedures

6.1.1.1. Study Entry

Volunteers who satisfy the entry criteria will be fully informed about the study by the investigator or his/her designee and asked whether they wish to participate. The information given to the patient or his/her legal representative will be in a language understandable to the volunteer or the representative. All questions will be answered prior to the volunteer signing consent. Written consent will be obtained from the volunteer or his/her legal representative prior to performing any study related procedures. This includes obtaining consent for the acquisition and review of the volunteer's prior medical history (and old medical record if appropriate and available). A copy of the informed consent will be given to the volunteer or his/her legal representative.

All volunteers having completed informed consent procedures will undergo a baseline screening evaluation within 30 days of initial immunization with the experimental candidate vaccine (or placebo). The CD4 cell count will be repeated on the day of initial immunization. These two observation points will define protocol baseline evaluation.

6.1.1.2. Study Duration

Each volunteer will complete a pre-immunization screening evaluation within 30 days prior to receiving the immunization series. Study procedures are outlined in [Table 4](#). Volunteers will be immunized with candidate vaccine or placebo on Days 0, 28 (week 4), 56 (week 8), and 168 (week 24). Volunteers will continue to undergo active protocol follow up visits on Days 182 (week 26), 196 (week 28), 252 (week 36), 294 (week 42) and 336 (week 48). The total trial time expected per volunteer is 336 days (48 weeks). The protocol recruitment period is expected to be approximately 16 weeks. The total trial duration is estimated to be approximately 72 weeks (18 months).

6.1.1.3. Study Evaluations

See also the Schedule of Assessments in [Table 4](#).

1. Study Visit 0, Day –30 to Day –3 (Week –4 to 0): Screening Visit

A screening evaluation will be performed within 3-30 days of the first immunization to determine eligibility for the study and to collect blood for baseline safety evaluation and immunological exams.

- a. Obtain informed consent for study prior to screening
- b. Obtain and record medical history including allergies, medications, and concomitant illnesses, and review of systems
- c. Counsel volunteer regarding avoiding HIV risk behaviors
- d. Perform complete physical examination, including vital signs, temperature, weight and height.
- e. Collect blood for CBC with differential, serum chemistries, liver function tests (including AST, ALT, alkaline phosphatase, total bilirubin), PT/PTT, CD4 cell count, Hepatitis B surface antigen, Hepatitis C antibody, HIV-1 ELISA/Western Blot, HIV-1 quantitative RNA PCR, and, in women, serum human chorionic gonadotropin (HCG) assay (See [Table 4](#) and [Section 11](#)).
- f. Collect urine for urinalysis
- g. Collect blood for baseline immunologic exams (See [Table 5](#) and [Section 12](#))

2. Study Visit 1, Day 0 (Week 0): First Immunization

- a. Obtain interim medical history since screening visit
- b. Perform physical examination, including vital signs, temperature, weight and height.
- c. Conduct urine pregnancy test (female volunteers).

If volunteer continues to meet inclusion/exclusion criteria he/she will be given a volunteer number, randomized, and the following will be done:

- d. Collect blood for safety labs (CBC with differential, serum chemistries, LFT's, CD4 cell count, and Quantitative HIV-1 RNA PCR) ([Table 4](#), [Table 5](#) and [Section 11](#)).
- e. Collect blood for immunologic studies ([Table 4](#) and [Table 5](#) and [Section 12](#)).
- f. Administer first injection of the study vaccine as an intramuscular injection in the deltoid muscle as per [Section 9.5](#).
- g. Record vital signs and examine injection site for local reactions at 15 and 30 minutes post-injection.
- h. Observe and instruct while volunteer takes own temperature and assesses local reactions (as a guide for subsequent evaluations at home).
- i. Counsel volunteer regarding avoiding HIV risk behaviors
- j. Dispense diary for immunization reactions ([Appendix 1](#)) and digital thermometer. Give instructions for diary completion and thermometer use.

3. Follow-up Phone contact by study nurse (24-48 hours after first immunization)

- a. Obtain interim history including: local and systemic reactions, post-injection oral temperature, Adverse Events, and concomitant medication.

4. **Study Visit 2, Day 14 (Week 2): Follow-up Clinical Visit**
 - a. Obtain interim medical history including: review of volunteer diary, adverse events, concomitant medications, and safety labs.
 - b. Perform exam of previous injection site and directed physical examination as indicated, including vital signs and temperature.
 - c. Counsel volunteer regarding avoiding HIV risk behaviors
 - d. Collect blood for safety labs and immunologic studies ([Table 4](#), [Table 5](#) and [Section 11](#)).
5. **Study Visit 3, Day 28 (Week 4): Second Immunization**
 - a. Obtain interim medical history including: adverse events, concomitant medications, and safety labs.
 - b. Perform exam of previous injection site and directed physical examination as indicated, including vital signs and temperature.
 - c. Conduct urine pregnancy test (female volunteers).
 - d. Collect blood for safety labs ([Table 4](#), [Table 5](#) and [Section 11](#)).
 - e. Collect blood for immunologic studies ([Table 4](#) and [Table 5](#) and [Section 12](#)).
 - f. Administer second injection of the study vaccine as an intramuscular injection in the deltoid muscle as per [Section 9.5](#).
 - g. Record vital signs and examine injection site for local reactions at 15 and 30 minutes post-injection.
 - h. Observe and instruct while volunteer takes own temperature and assesses local reactions (as a guide for subsequent evaluations at home).
 - i. Counsel volunteer regarding avoiding HIV risk behaviors
 - j. Dispense diary for immunization reactions ([Appendix 1](#)). Give instructions for its completion and for digital thermometer use.
6. **Follow-up Phone contact by study nurse (24-48 hours after second immunization)**
 - a. Obtain interim history including: local and systemic reactions, post-injection oral temperature, Adverse Events, and concomitant medication.
7. **Study Visit 4, Day 42 (Week 6): Follow-up Clinical Visit**
 - a. Obtain interim medical history including: review of volunteer diary, adverse events, concomitant medications, and safety labs.
 - b. Perform exam of previous injection site and directed physical examination as indicated, including vital signs and temperature.
 - c. Counsel volunteer regarding avoiding HIV risk behaviors
 - d. Collect blood for safety labs and immunologic studies ([Table 4](#) and [Table 5](#) and [Section 11](#) and [Section 12](#)).
8. **Study Visit 5, Day 56 (Week 8): Third Immunization**
 - a. Obtain interim medical history including: adverse events, concomitant medications, and safety labs.
 - b. Perform exam of previous injection site and directed physical examination as indicated, including vital signs and temperature.
 - c. Conduct urine pregnancy test (female volunteers).

- d. Collect blood for safety labs ([Table 4](#), [Table 5](#) and [Section 11](#)).
 - e. Collect blood for immunologic studies ([Table 4](#) and [Table 5](#) and [Section 12](#)).
 - f. Administer third injection of the study vaccine as an intramuscular injection in the deltoid muscle as per [Section 9.5](#).
 - g. Record vital signs and examine injection site for local reactions at 15 and 30 minutes post-injection.
 - h. Observe and instruct while volunteer takes own temperature and assesses local reactions (as a guide for subsequent evaluations at home).
 - i. Counsel volunteer regarding avoiding HIV risk behaviors
 - j. Dispense diary for immunization reactions ([Appendix 1](#)). Give instructions for its completion and digital thermometer use.
- 9. Follow-up Phone contact by study nurse (24-48 hours after third immunization)**
- a. Obtain interim history including: local and systemic reactions, post-injection oral temperature, Adverse Events, and concomitant medication.
- 10. Study Visit 6, Day 70 (Week 10): Follow-up Clinical Visit**
- a. Obtain interim medical history including: review of volunteer diary, adverse events, concomitant medications, and safety labs.
 - b. Perform exam of previous injection site and directed physical examination as indicated, including vital signs and temperature.
 - c. Counsel volunteer regarding avoiding HIV risk behaviors
 - d. Collect blood for safety labs and immunologic studies ([Table 4](#) and [Table 5](#) and [Section 11](#) and [Section 12](#)).
- 11. Study Visit 7, Day 84 (Week 12): Follow-up Clinical Visit**
- a. Obtain interim medical history including: adverse events, concomitant medications, and safety labs.
 - b. Perform directed physical examination as indicated, including vital signs and temperature.
 - c. Counsel volunteer regarding avoiding HIV risk behaviors
 - d. Collect blood for safety labs and immunologic studies ([Table 4](#) and [Table 5](#) and [Section 11](#) and [Section 12](#)).
- 12. Study Visit 8, Day 112 (Week 16): Follow-up Clinical Visit**
- a. Obtain interim medical history including: adverse events, concomitant medications, and safety labs.
 - b. Perform directed physical examination as Indicated, including vital signs and temperature.
 - c. Counsel volunteer regarding avoiding HIV risk behaviors
 - d. Collect blood for safety labs and immunologic studies ([Table 4](#) and [Table 5](#) and [Section 11](#) and [Section 12](#)).

13. Study Visit 9, Day 168 (Week 24): Fourth Immunization

- a. Obtain interim medical history including:., adverse events, concomitant medications, and safety labs.
- b. Perform exam of previous injection site and directed physical examination as indicated, including vital signs and temperature.
- c. Counsel volunteer regarding avoiding HIV risk behaviors
- d. Conduct urine pregnancy test (female volunteers).
- e. Collect blood for safety labs (Table 4, Table 5 and Section 11).
- f. Collect blood for immunologic studies (Table 4 and Table 5 and Section 12).
- g. Administer fourth injection of the study vaccine as an intramuscular injection in the deltoid muscle as per Section 9.5.
- h. Record vital signs and examine injection site for local reactions at 15 and 30 minutes post-injection.
- i. Observe and instruct while volunteer takes own temperature and assesses local reactions (as a guide for subsequent evaluations at home).
- j. Dispense diary for immunization reactions (Appendix 1) Give instructions for its completion and for thermometer use.

14. Follow-up Phone contact by study nurse (24-48 hours after fourth immunization)

- a. Obtain interim history including: local and systemic reactions, post-injection oral temperature, Adverse Events, and concomitant medication.

15. Study Visit 10, Day 182 (Week 26): Follow-up Clinical Visit

- a. Obtain interim medical history including: review of volunteer diary, adverse events, concomitant medications, and safety labs.
- b. Perform exam of previous injection site and directed physical examination as indicated, including vital signs and temperature.
- c. Counsel volunteer regarding avoiding HIV risk behaviors
- d. Collect blood for safety labs and immunologic studies (Table 4 and Table 5 and Section 11 and Section 12).

16. Study Visit 11, Day 196 (Week 28): Follow-up Clinical Visit

- a. Obtain interim medical history including:., adverse events, concomitant medications, and safety labs.
- b. Perform directed physical examination as indicated, including vital signs and temperature.
- c. Counsel volunteer regarding avoiding HIV risk behaviors
- d. Collect blood for safety labs and immunologic studies (Table 4 and Table 5 and Section 11 and Section 12).

17. Study Visit 12, Day 252 (Week 36): Follow-up Clinical Visit

- a. Obtain interim medical history including: adverse events, concomitant medications, and safety labs.
- b. Perform directed physical examination as indicated, including vital signs and temperature.
- c. Counsel volunteer regarding avoiding HIV risk behaviors
- d. Collect blood for safety labs and immunologic studies ([Table 4](#) and [Table 5](#) and [Section 11](#) and [Section 12](#)).

18. Study Visit 13, Day 294 (Week 42): Follow-up Clinical Visit

- a. Obtain interim medical history including: adverse events, concomitant medications, and safety labs.
- b. Perform directed physical examination as indicated, including vital signs and temperature.
- c. Counsel volunteer regarding avoiding HIV risk behaviors
- d. Collect blood for safety labs and immunologic studies ([Table 4](#) and [Table 5](#) and [Section 11](#) and [Section 12](#)).

19. Study Visit 14, Day 336 (Week 48): Follow-up Clinical/End of Study Visit

- a. Obtain interim medical history including: review adverse events, concomitant medications, and safety labs.
- b. Perform complete physical examination, including vital signs, temperature, weight and height.
- c. Counsel volunteer regarding avoiding HIV risk behaviors
- d. Conduct urine pregnancy test (female volunteers).
- e. Collect blood for safety labs ([Table 4](#) and [Section 11](#)).
- f. Collect urine for urinalysis.
- g. Collect blood for immunologic studies ([Table 4](#) and [Table 5](#) and [Section 12](#)).

6.1.1.4. Missed Visits

A volunteer is considered to have missed a visit if (s)he is not seen in ± 7 days of a scheduled study visit through the first 3 immunizations and within ± 28 days of a scheduled study visit after the third immunization visit. Volunteers who miss one of the immunization visits will be kept on the study if (s)he is willing and it is deemed appropriate by the investigator. Volunteers who miss 2 immunization visits will be removed from the study and may be replaced at the discretion of the investigator.

6.1.1.5. Replacement

A volunteer who drops out of the study for any reason other than toxicity (an SAE related to the study drug) may be replaced. No replacements will be allowed when the enrollment is closed. Volunteers who fail to return for two clinic visits after day 14 may be considered to be dropouts and can be replaced at the discretion of the Investigator. Volunteers who miss one of the first 3 immunization visits can be replaced at the discretion of the Principal Investigator. They will

continue to be evaluated for safety and will be evaluable for immunogenicity up to their last vaccine administration date. Volunteers who miss 2 immunization visits will be removed from the study and may be replaced at the discretion of the investigator. Volunteers with missed vaccination visits will be included in all safety analyses.

6.1.1.6. Pregnancy

In the event of pregnancy while the volunteer is on study, no further immunizations will be given regardless of outcome. The volunteer will be followed for all remaining scheduled visits according to the schedule of procedures for safety evaluation. The site will maintain contact with pregnant volunteers to obtain pregnancy outcome information.

6.1.1.7. Off-study evaluations

In the event a volunteer discontinues participation in the study prematurely, the initial off study evaluation will be treated as an end of study visit and consist of a complete physical examination, follow-up clinical assessment, selected blood chemistry and hematology evaluations, CD4+ count, ultra-sensitive viral load, PBMC and sera for immunogenicity assays (batched), PMBC stored (< -135° C) for assessment of chemokine receptor expression and chemokine production capacity. Patients who withdraw prematurely from the study (prior to the completion of the 32 weeks of study) will have all safety tests performed as soon as possible. Follow up off study evaluations may be conducted if agreed to by volunteer per schedule visit outline in [Table 4](#) to allow for additional safety and immunogenicity evaluation to be completed. However, immunization will not be permitted once a volunteer has discontinued participation in the study. The Investigator will attempt to complete all discharge procedures and will follow each dropout (by telephone if necessary) for adverse experiences through 24 weeks after his/her first vaccine injection.

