6.3. Treatment Assignment

The volunteers in this study will enroll in each group of the study sequentially as this is a dose escalation study. Each volunteer will undergo randomization as described in [Section 8.4](#). Each group will be fully enrolled prior to the enrollment of the next group. The description of the FLSC vaccine is noted in [Section 8](#) and [Section 9](#) and the clinical formulation of the products are listed in [Section 9](#). Volunteers in all arms will be immunized by intramuscular injection on Days 0, 28 (week 4), 56 (week 8), and 168 (week 24). Following completion of the immunization schedule, all volunteers will be followed (for an additional 24 weeks) until the end of the trial at 48 weeks as detailed in [Section 6.1.1.3](#).

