7.3.1.1. Conditions mandating withdrawal from the Study

Individual volunteers will be withdrawn from further immunizations on the study for the following reasons:

- Experiencing a grade 4 toxicity/adverse event or serious adverse event considered by the principal investigator to be related to study vaccine
- Becoming pregnant during the study
- Requiring cytotoxic chemotherapy or immunomodulatory therapy during the course of the study
- Missing 2 immunization visits (injections)

Note that those withdrawn for toxicity reasons will continue to be followed for safety as described in [Section 6.1.1.7](#).

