7.3.2.3. Volunteer Withdrawn for Vaccine Related Toxicity

Should a volunteer be discontinued from the study for toxicity reasons, the volunteer will continue to have safety visits performed until the end of the study as in [Section 6.1.1.7](#).

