11.4. Recording Adverse Events

Adverse events spontaneously reported by the volunteer and/or in response to an open question from the study personnel or revealed by observation will be recorded during the study at the investigational site. However, abnormal values that constitute an SAE or lead to discontinuation of administration of study drug must be reported and recorded

as an AE. Information about AEs will be collected from signing of consent until the end of the study. Serious Adverse Event information will be collected from signing of consent until 24 weeks following the last dose of study drug. The AE term should be reported in standard medical terminology when possible. For each AE, the investigator will evaluate and report the onset (date and time), resolution (date and time), intensity, causality (as defined in [Section 11.3](#)), action taken, serious outcome (if applicable), and whether or not it caused the patient to discontinue the study.

All adverse events occurring during the trial must be evaluated by the investigator and graded according to the adverse experience grading table ([Appendix 2](#)).

It is important to distinguish between serious and severe AEs. Severity is a measure of intensity whereas seriousness is defined by the criteria under [Section 11.2.1.2](#). An AE of severe intensity may not be considered serious.

Should a pregnancy occur, it must be reported and recorded on the Institute of Human Virology's pregnancy form. Pregnancy in itself is not regarded as an AE unless there is a suspicion that an investigational product may have interfered with the effectiveness of a contraceptive medication. However, it is a criterion for stopping immunizations in a volunteer as noted in [Section 6.1.1.6](#) and [Section 7.3.1.1](#).

The outcome of all pregnancies (spontaneous miscarriage, elective termination, normal birth or congenital abnormality) must be followed up and documented even if the patient was discontinued from the study.

All reports of congenital abnormalities/birth defects are SAEs. Spontaneous miscarriages should also be reported and handled as SAEs. Elective abortions without complications should not be handled as AEs.

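### Section 6.1.1.7 counts adverse-event follow-up of dropouts from the first injection, so it ends nominally on the day of dose 4 and conflicts with five other parts of the protocol

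*Combined protocol and SAP*

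**What the plan says.** Section 6.1.1.7 (Off-study evaluations) gives a volunteer who stops early one evaluation, handled as an end of study visit and including a CD4 count. Later off-study visits are optional. The investigator then follows each dropout, by telephone if need be, "for adverse experiences through 24 weeks after his/her first vaccine injection".

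Section 6.3 puts the four injections on Days 0, 28, 56 and 168. For those who complete the series, "all volunteers will be followed (for an additional 24 weeks) until the end of the trial at 48 weeks".

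Other parts of the protocol set different periods:

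- Synopsis, safety criteria: reactions and adverse experiences are monitored for 12 months after the first injection.
- 7.3.2.3: after withdrawal for vaccine-related toxicity, "the volunteer will continue to have safety visits performed until the end of the study". The sentence cites 6.1.1.7 as its source.
- 11.2.1.1 and 11.2.1.2: AEs and SAEs are recorded up to 84 days after immunization or treatment stops, and only while the volunteer is on the protocol.
- 11.4: AEs are collected to the end of the study. For SAEs, "Serious Adverse Event information will be collected from signing of consent until 24 weeks following the last dose of study drug".
- Section 17, investigator responsibilities: SAEs on study or within 30 days of withdrawal are recorded.

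Two lesser wording differences sit beside these. Section 6.1.1.7 describes premature withdrawal as "prior to the completion of the 32 weeks of study", while 7.3.2 defines completion as 48 weeks. Section 6.1.1.4 says "Volunteers who miss 2 immunization visits will be removed from the study" (6.1.1.5 agrees), while 7.3.1.1 lists the same event under "Individual volunteers will be withdrawn from further immunizations on the study for the following reasons".

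**The concern.** Safety is the primary objective, and each dose level has only 15 vaccine recipients. A follow-up limit counted from the first injection shortens with every dose given and nominally reaches zero at dose 4, when exposure is greatest. Some volunteers who leave after that dose may have left because of how they felt. Non-serious events with onset after their off-study visit need not be sought under 6.1.1.7, and any loss would make the vaccine look safer.

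The conflict is also a practical one. Site staff dealing with a dropout meet several end dates and have no rule saying which prevails. Different staff could apply different windows, and recorded AE rates would then depend partly on which section was read.

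CD4 decline needs separate thought, because anti-CD4 responses are the protocol's stated theoretical risk (4.5.2 and section 11). The halting rules in 6.4.1 and 7.3.3 count a decline only if it is confirmed by assays at least 4 weeks apart. A decline first seen at the off-study visit could not be confirmed unless the volunteer agreed to an optional later visit.

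**Working it through.** **Inputs.** Injections on Days 0, 28, 56 and 168, and study end at week 48 (6.3). Dropout AE limit of 24 weeks from the first injection (6.1.1.7). Visit window of ±28 days after the third immunization (6.1.1.4). SAE window of 24 weeks from the last dose (11.4). SAE window of 30 days from withdrawal (section 17).

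**The plan's own calendar.** 24 × 7 = 168, the nominal day of dose 4. 168 + 168 = 336, and 336 / 7 = 48 weeks. The schedule in 6.3 is reproduced.

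**Days of AE follow-up after the last dose under 6.1.1.7** = 168 − day of last dose:

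| Last dose received | Day | Days left |
|---|---|---|
| 1 | 0 | 168 |
| 2 | 28 | 140 |
| 3 | 56 | 112 |
| 4 | 168 | 0 |

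**Effect of the visit window.** Dose 4 may fall between Day 140 (168 − 28) and Day 196 (168 + 28). The remainder runs from 168 − 140 = +28 days to 168 − 196 = −28 days. In the second case the limit passes before the injection is given.

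**Dropouts after dose 4 given on Day 168.** Remaining days at each later scheduled visit:

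| Dropout day | AE days left, 6.1.1.7 | SAE days left, 11.4 (336 − day) | Last day of 30-day SAE rule, section 17 |
|---|---|---|---|
| 182 | 0 | 154 | 212 |
| 196 | 0 | 140 | 226 |
| 252 | 0 | 84 | 282 |
| 294 | 0 | 42 | 324 |

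The middle columns are different event classes. The 11.4 figure shows that SAE collection continues; it is not an AE window from which 6.1.1.7 falls short. The AE rule in 11.4 is the end of the study. The 84-day windows in 11.2.1 would run to Day 252 (168 + 84), but they apply only while the volunteer is on the protocol, so they do not clearly reach a dropout.

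**Weight of one volunteer.** One missed event in a dose group is 1/15 = 6.7 percentage points; pooled over vaccine recipients it is 1/45 = 2.2 points. This is the unit of error, not an estimate of how often it would occur.

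**Secondary wording.** Week 32 is Day 224 (32 × 7), so a withdrawal between weeks 32 and 48 falls outside the sentence on prompt safety tests. A volunteer who misses two immunization visits has a nominal last dose no later than Day 56 (doses 2 and 4 missed), and so keeps at least 112 days under 6.1.1.7.

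**The case against.** A reader might infer that a late dropout has no required follow-up at all after the last injection. The documents do not support that:

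- The off-study evaluation in 6.1.1.7 comes after dose 4 for anyone who leaves after dose 4. It includes a physical examination, laboratory tests and a CD4 count, and a footnote to Table 4 repeats the requirement for early withdrawal.
- SAEs remain covered by 11.4 and section 17.
- Withdrawals for vaccine-related toxicity have safety visits to the end of the study under 7.3.2.3.

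What remains is non-serious events after the off-study visit, in volunteers who received dose 4 and were not withdrawn for toxicity.

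Four further limits are fair. Early reactions to dose 4 are largely captured by the 24 to 48 hour contact and the 7-day diary (11.1.5.6), so the exposure is mainly to late-onset events. A volunteer who declines the end of study visit has no further study activity (7.3.2.1), and no new window changes that. Section 13.3.1.3 already concedes that withdrawal may lead to underestimation. It would also be too strong to say that a CD4 decline after dose 4 would go unrecorded: one count is taken at the off-study visit, and the difficulty is confirming it.

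A reader might also take the 32-week phrase or the missed-dose wording as support for the dose-4 gap. Neither is. The first touches only a sentence on prompt testing, and the second concerns volunteers who did not receive a full series.

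Two things survive. The general AE rule in 11.4 does not mention dropouts while 6.1.1.7 does, so the shorter limit is the one a site would probably apply. And 7.3.1.1, 11.5.1 and 11.5.2 all send adverse-event withdrawals to 6.1.1.7 for follow-up, while 6.1.1.5 glosses toxicity as an SAE related to the study drug. A volunteer who leaves over non-serious reactions may therefore not have the protection of 7.3.2.3.

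**Conclusion.** The concern holds in a limited form. Under 6.1.1.7 a non-toxicity dropout after dose 4 nominally has no days of required follow-up for non-serious AEs beyond the off-study evaluation; the allowed visit window moves that figure between +28 and −28 days. Dropouts last dosed at dose 1, 2 or 3 keep 168, 140 or 112 days. The limit conflicts with the synopsis, 7.3.2.3, 11.2.1, 11.4 and section 17.

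AE rates after dose 4 may be underestimated if late dropouts occur. The documents give no dropout rate and no rate of late non-serious events, so the size of any bias is unknown. The conclusion rests on reading 6.1.1.7 as the governing rule for dropouts. If the end-of-study AE rule in 11.4 was meant to govern, the gap closes but the contradiction in the text remains. This should be corrected. It does not by itself undermine the safety analysis.

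**What to change.** Reconcile the synopsis, 6.1.1.7, 7.3.2.3, 11.2.1, 11.4 and section 17 to one AE and one SAE data-collection window for dropouts. Count both from the last injection rather than the first, as 11.4 already does for SAEs. The sponsor sets the length, which should be stated once and cross-referenced elsewhere. Make 6.1.1.7 agree with 7.3.2.3, which now cites it for a rule it does not contain, and say which withdrawals count as toxicity. All of this is subject to the volunteer's consent.

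State how a CD4 decline first seen at an off-study visit will be reported and counted when no later sample is obtained. Telephone contact cannot supply the second assay; that needs one of the optional visits.

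In the same edit, reconcile the 32-week phrase in 6.1.1.7 with the 48-week completion definition in 7.3.2. Also reconcile removal from the study (6.1.1.4, 6.1.1.5) with withdrawal from immunizations (7.3.1.1) for volunteers who miss two doses; 6.1.1.5 keeps those with missed vaccinations in all safety analyses.

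The cost is protocol wording, telephone calls and optional safety visits for a few dropouts. No dose or immunization rule changes.
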